## 9 CLINICAL MONITORING

The Purpose of the monitoring plan is to present the [name] Lab's approach to monitoring clinical trials. The plan facilitates compliance with good clinical practice.

- (a) The rights and well-being of human subjects are protected.
- (b) The reported trial data are accurate, complete, and verifiable from source documents.
- (c) The conduct of the trial is in compliance with the currently approved protocol/amendment(s), with GCP, and with applicable regulatory requirement(s).

This section identifies key monitoring activities and specifies the data to be reviewed over the course of a clinical trial. This is a single site, investigator initiated, clinical trial so there will be no site monitoring plan in place.

### [name] Lab Monitoring Plan

The latest version of the approved IRB application for this clinical trial will be followed at all times. This responsibility falls in the hands of the study coordinator and research assistants. If at any time there is a deviation from protocol, the deviation from protocol log (*Appendix H*) will be filled out. All team members will be trained on how and when to use this log. The most up to date IRB application will be on file at the Clinical Trials desk in [name]. Deviations will be sent to IRB every 4-6 weeks (if necessary).

The PI will always be available by phone or email to the study coordinator or research assistant in the case of an adverse event. The study coordinator or research assistant will keep the PI up to date on all occurrences throughout the study's continuation in a timely manner, making sure the PI is aware of any events as soon as possible.

AE and SAE are clearly defined in the Master Protocol. Documents of AE and SAE can be found in the study binder on file at the Clinical Trials desk in [name]. It is responsibility of the study coordinator to report all events to the PI. For our practices we have adapted the decision tree provided by UNC-CH IRB to assist with reporting of such events (*Attachment 7*). The PI will have read-only access to the redcap data base for this study. At any time the PI can check and make sure that data entry is complete and accurate for each participant. This

allows the PI to view reports that provide information on any missing data on an individual participant basis, but does not allow them to add, change or input any data.

## 10 STATISTICAL CONSIDERATIONS

### 10.1 STUDY HYPOTHESES

We hypothesize that

- (1) Daily tACS stimulation for 5 days reduces auditory hallucination symptoms as measured by the AHRS, PANSS and BACS survey instruments, and that
- (2) weekly tACS stimulation during a follow-up maintenance regimen extends the duration of that clinical benefits as measured by the AHRS, PANSS and BACS.

We hypothesize that

- (1) baseline impairment in EEG oscillations and connectivity predicts treatment success, and that
- (2) changes in these markers are correlated with improvement of clinical symptom presentation as measured by the AHRS, PANSS, and BACS.

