
	the EEG data, we will also be collecting ECG data. An sMRI visit will be scheduled between the end of the 5 th day of stimulation, and the first maintenance stimulation session.
Objectives	
Our primary objective is to conduct a randomized clinical trial to investigate the ability of tACS to renormalize pathological alpha oscillations in dl-PFC of patients with schizophrenia and schizoaffective disorder and experiencing auditory hallucinations by comparing sham and active treatment regimens in terms of longitudinal changes in AHRS scores and other measures. We also aim to evaluate the ability of an 8-week maintenance regimen to prolong the duration of stimulation-induced clinical benefits in terms of longitudinal changes in AHRS scores and other measures. We hypothesize that (1) tACS reduces auditory hallucination symptoms after 5 consecutive days of daily stimulation and (2) repeat application of tACS during a follow-up maintenance regimen extends the duration of the clinical benefits of the initial stimulation.
 
Our secondary objective is to collect further data demonstrating the value of oscillations and connectivity measures derived from EEG data as novel biomarkers in the treatment of medication refractory auditory hallucinations in schizophrenia with transcranial current stimulation. To reach this objective, we will test the working hypothesis that (1) baseline impairment in EEG oscillations and connectivity predicts treatment success, and (2) changes in these markers correlate with improvement of clinical symptom presentation as measured by the AHRS, PANSS (Attachment 5), and BACS (Attachment 6). We will collect data to support our working hypothesis by measuring whole-head EEG data with individual locations of scalp electrodes and structural MRI from all patients in our study (40 patients from Aim 1) before and immediately after the five day course of stimulation and at each maintenance stimulation visits for weeks 1, 3 and 8.

End date	December 2020

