## SCHEMATIC OF STUDY DESIGN

At enrollment, the 40 eligible enrollees will be allocated by randomization to four treatment-sequence groups: tACS-tACS, tACS-sham, sham-sham, sham-tACS) (10 participants per sequence). The randomization will be stratified by sex.

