Here,  $\bar{Y}(t_0)$  is the average of all baseline values. The expected value is shown in **Table 1** below. The fitted model will be used to tabulate statistical estimates (all with 95% confidence intervals) of the population parameters of interest: variance components, intra-class correlation, the direct effect of treatment ( $\mu_S - \mu_A$ ) in period 1, treatment-specific period effects ( $\tau_A, \tau_S$ ), and a longer-term treatment effect ( $\lambda$ ) that carries over from period 1 into period 2. Parameters  $\tau_A$  and  $\tau_S$  represent both the period-by-treatment interaction and also the 'period effect' ( $\tau_A + \tau_S$ ). In a 2-sequence crossover design, parameters  $\tau_A, \tau_S$  and  $\lambda$  would be aliased together; whereas, in the 4-sequence design they are not aliased. For the main analysis we assume carryover effect  $\lambda$  vanishes in the later weeks of the maintenance regimen in period 2; that is, effects of any treatments in period 1 have washed out by the end of the maintenance regimen. (That would not be the case if treatment A in period 1 cured the patient.) The sensitivity of the main results to this assumption will be investigated in auxiliary sensitivity analyses. In this model, the direct treatment effect in period 1 is  $(\mu_S - \mu_A)$  while the direct treatment effect in period 2 is  $((\mu_S + \tau_S) - (\mu_A + \tau_A))$ . We conjecture that  $\tau_S \approx 0$  and that  $\tau_A$  has a small negative value owing to weekly stimulation having a somewhat smaller effect than daily stimulation. The magnitude of  $\tau_S$  is of interest because it represents the efficacy of montly stimulation relative to daily stimulation. The magnitude of  $\lambda$  is of interest because it represents impact of treatment that endures into (at least) the beginning of the maintenance regimen.

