**Table 1. Conditional expected value of change from baseline evaluated at the average baseline value**

		Treatment Sequence			
		SS	SA	AS	AA
Period 1	$t_1$	$m_S$	$m_S$	$m_A$	$m_A$
	$t_2$	$m_S + \tau_S$	$m_A + \tau_A$	$m_S + \tau_S + \lambda$	$m_A + \tau_A + \lambda$
	$t_3$	$m_S + \tau_S$	$m_A + \tau_A$	$m_S + \tau_S + \lambda$	$m_A + \tau_A + \lambda$
	$t_4$	$m_S + \tau_S$	$m_A + \tau_A$	$m_S + \tau_S + \lambda$	$m_A + \tau_A + \lambda$
	$t_5$	$m_S + \tau_S$	$m_A + \tau_A$	$m_S + \tau_S + \lambda$	$m_A + \tau_A + \lambda$
	$t_6$	$m_S + \tau_S$	$m_A + \tau_A$	$m_S + \tau_S$	$m_A + \tau_A$
	$t_7$	$m_S + \tau_S$	$m_A + \tau_A$	$m_S + \tau_S$	$m_A + \tau_A$
	$t_8$	$m_S + \tau_S$	$m_A + \tau_A$	$m_S + \tau_S$	$m_A + \tau_A$
	$t_9$	$m_S + \tau_S$	$m_A + \tau_A$	$m_S + \tau_S$	$m_A + \tau_A$

For the primary analysis, the above model will be fitted using only AHRS scores at  $t \in \{t_1, t_9\}$  assuming  $\lambda=0$ :

$$E[\Delta Y_{ij}(t) | \mathbf{X}, Y_{ij}(t_0)] = \mu_S X_1 + \mu_A X_2 + \tau_S X_3 + \tau_A X_4 + \beta (Y_{ij}(t_0) - \bar{Y}(t_0))$$

The set of sensitivity analyses will include fitting the model using AHRS scores at  $t \in \{t_1, t_6, t_7, t_8, t_9\}$  (with  $\lambda=0$ ), which is anticipated to provide more precision and power for analysis of the treatment effects.

The analyses will focus on the point estimates and confidence interval estimates of the parameters of interest; for example,  $(\mu_S - \mu_A)$  and  $((\mu_S + \tau_S) - (\mu_A + \tau_A))$ . The data and the fitted model will be visualized via graphical figures. The fitted model using only AHRS scores at  $t \in \{t_1, t_9\}$  will be used to test the primary null hypothesis,  $H_0: "(\mu_S - \mu_A) = 0 \text{ and } (\tau_S - \tau_A) = 0"$ , using an F-test of size  $\alpha = 0.05$ .

To explore carryover of treatment effects, the model

$$E[\Delta Y_{ij}(t) | \underline{X}, Y_{ij}(t_0)] = \mu_S X_1 + \mu_A X_2 + \tau_S X_3 + \tau_A X_4 + \lambda X_5 + \beta (Y_{ij}(t_0) - \bar{Y}(t_0))$$

will be fitted using AHRS scores recorded on occasions  $t \in \{t_1, t_2, t_3, t_4, t_5, t_6, t_7, t_8, t_9\}$ .

Sensitivity analyses will be used to evaluate the robustness of the main results to reasonable perturbations of the methods and assumptions used. This set of analyses will examine goodness of fit diagnostics for the linear model, and will include modified versions of the main analyses.

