Based on **Table 2** estimates for AHRS, we anticipate that 20 participants per regimen in period 1 will provide a margin of error of about 1.0 AHRS unit for regimen-specific estimates of mean change from baseline; i.e., we anticipate a 95% C.I. of the form [mean change  $\pm$  1.0] for each regimen.

For the primary analysis, the model will be fitted using only AHRS scores at  $t \in \{t_1, t_0\}$ :

$$E[\Delta Y_{ij}(t) | X, Y_{ij}(t_0)] = \mu_S X_1 + \mu_A X_2 + \tau_S X_3 + \tau_A X_4 + \beta (Y_{ij}(t_0) - \bar{Y}(t_0))$$

We will test  $H_0: "(\mu_S - \mu_A) = 0 \text{ and } (\tau_S - \tau_A) = 0"$ , using an F-test of size  $\alpha = 0.05$ . However, for purposes of the analysis of anticipated power, we considered a close surrogate: testing  $H_0: "(\mu_S - \mu_A) = 0"$  and  $H_0: "(\tau_S - \tau_A) = 0"$  separately using F-tests each of size  $\alpha = 0.025$ . In **Figure 2**, power curves are for the test of  $H_0: "(\mu_S - \mu_A) = 0"$ .

The curves are based on the point-estimates and 95% C.I. estimates of intra-subject and inter-subject variance components expressed here as standard deviations (by taking square roots) which are in turn based on the data in Table 2 and based on a conjectured underlying correlation of 0.90 between  $t_0$  and  $t_1$ .

[figure not shown]
[figure not shown]
The probability ('power') of drawing a sample that yields a p-value  $< \alpha = 0.025$  is a function of the unknown magnitude of the treatment effect ( $\mu_S - \mu_A$ ) in the target population. In **Figure 2**, for example, if our conjectures and assumptions are true and in truth  $(\mu_S - \mu_A) = 1.18$  AHRS units, the likelihood of rejecting  $H_0: (\mu_S - \mu_A) = 0$ " is estimated to be 90% with C.I. [50%, 99%]. For comparison, **Figure 1** provides power curves for a test of  $H_0: (\mu_S - \mu_A) = 0$ " based on only the data from period 1 --an approach that does not take advantage of the crossover design.

**Figure 3** provides similar information for test of  $H_0: (\mu_S - \mu_A) = 0$ " based on AHRS scores recorded on occasions  $t \in \{t_1, t_6, t_7, t_8, t_9\}$  assuming carryover effect  $\lambda$  has vanished before  $t_6$ . Inclusion of the carryover effect in the model can reduce precision and power for the test of treatment effects.

When exploring carryover effects using scores from occasions  $t \in \{t_1, t_2, t_6, t_7, t_8, t_9\}$  to fit

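### The week-8 maintenance effect averages AA-AS with SA-SS, so it does not isolate the prolongation in Hypothesis 2 and is half its size if maintenance only prolongs an existing benefit

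*Combined protocol and SAP*

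**What the plan says.** Section 10.1 states Hypothesis 2 as "weekly tACS stimulation during a follow-up maintenance regimen extends the duration of that clinical benefits". The Objectives in the Protocol Summary are more explicit about which benefit is meant: "repeat application of tACS during a follow-up maintenance regimen extends the duration of the clinical benefits of the initial stimulation". Participants are allocated equally to SS, SA, AS and AA, "10 participants per sequence".

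Section 10.2, Aim 1, assumes for the main analysis that "effects of any treatments in period 1 have washed out by the end of the maintenance regimen". Below Table 1: "For the primary analysis, the above model will be fitted using only AHRS scores at" t1 and t9, with the carryover term λ set to zero. The t9 row of Table 1 then holds only two means: m_S + τ_S for SS and AS, and m_A + τ_A for SA and AA. The direct treatment effect in period 2 is defined as (μ_S + τ_S) - (μ_A + τ_A). The primary test is a joint F-test at 0.05 of μ_S - μ_A = 0 and τ_S - τ_A = 0.

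Two further models are listed. One uses t1 and t6 to t9 with λ = 0. The other, exploratory, uses t1 to t9 and adds the same λ to AS and AA at t2 to t5. Neither has an initial-by-maintenance term, and no AA versus AS contrast is specified anywhere.

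**The concern.** Only AS and AA participants receive the active five-day course, so only they have a stimulation benefit to extend. The period-2 effect draws half its weight from SA versus SS, where there is none. The same pooled value can arise because maintenance prolongs the initial benefit, because weekly tACS works by itself, or from a mixture of the two.

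This is a separate issue from wash-out. AS can wash out completely and the constraint AA-AS = SA-SS remains. The additive λ in the exploratory model does not lift it either, because λ cancels from AA-AS.

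At stake is what can be said about Hypothesis 2. A true prolongation effect would be diluted and might be reported as inconclusive. A pooled effect driven by SA-SS could be taken as support for prolongation. The randomised groups needed to tell these apart are already in the design.

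**Working it through.** Contrasts are signed so that benefit is positive.

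**Inputs.** From section 10.3, Table 2: mean changes -2.29 (sham) and -3.75 (tACS); variance of change 5.82; conditional variance 5.53, split 4.98 between and 0.55 within subjects; correlation 0.90 (the plan's conjecture). Ten per sequence. Assumptions made here: d = 3.75 - 2.29 = 1.46, and the 0.90 correlation also holds between t1 and t9.

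**Plan's own figure.** Generalised least squares for the {t1, t9} model with components 4.98 and 0.55 gives SE(μ_S - μ_A) = 0.323. For an effect of 1.18 at α = 0.025, the noncentral F with 37 df gives 90.0%. At the confidence limits of the variance components it gives 99.4% and 49.7%. This reproduces the stated 90% [50%, 99%].

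**Standard errors at t9**, with v = 5.53 and ρ = 0.90, so v(1 - ρ²) = 5.53 × 0.19 = 1.051:
- pooled period-2 effect: √(1.051 × 0.1) = 0.324
- AA-AS adjusted for t1: √(1.051 × 0.2) = 0.458
- (AA-AS)-(SA-SS): √(1.051 × 0.4) = 0.648

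**Expectation under pure prolongation** (AA keeps d; SA, AS and SS at 0). Pooled: (1.46 + 0)/2 = 0.73 = d/2. This does not depend on ρ. The t1, t6-t9 model and the all-occasion λ model also return d/2. With sequence sizes such as 8/12/9/11 or 11/9/12/8 the factor stays at 0.49 to 0.50.

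**Effect on the week-1 estimate.** The constraint also ignores the difference at t9 between those who had active and sham week 1, which is d/2 here. The fitted μ_S - μ_A becomes d - ρ × d/2 = 1.46 - 0.90 × 0.73 = 0.80.

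**Non-identifiability.** With a week-1 effect of 1.46, the t9 benefits (SS, SA, AS, AA) = (0, 0, 0, d) and (0, d, d, d) give the same fit: μ_S - μ_A = 0.80 and period-2 effect 0.73. AA-AS is 1.46 in the first pattern and 0 in the second.

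**Power for d = 1.46** (noncentral F; 36 df for pooled; 17 df for AA-AS within its 20 participants):

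| Scenario | ρ | α | Pooled | AA-AS |
|---|---|---|---|---|
| Pure prolongation | 0.90 | 0.05 | 59% | 85% |
| Pure prolongation | 0.90 | 0.025 | 47% | 76% |
| Weekly tACS works equally without initial course | 0.90 | 0.05 | 99% | 85% |
| Pure prolongation | 0.56 | 0.05 | 25% | 41% |
| Weekly tACS works equally without initial course | 0.56 | 0.05 | 72% | 41% |

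The rows at 0.56 use the variance implied by Table 2's own formulas: σ²(1 - ρ²) = 5.82(1 + ρ)/2 = 5.82 × 1.56/2 = 4.54. In a joint model with about 35 df, AA-AS reaches 87% rather than 85% at ρ = 0.90 and α = 0.05.

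Under pure prolongation at ρ = 0.90 and α = 0.05, the difference (AA-AS)-(SA-SS) has expectation 1.46 and power about 59%.

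**The case against.** Four points on the other side carry weight.

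1. AA versus AS is a reading of Hypothesis 2; the documents never write that contrast. Aim 1 asks more broadly about the relative efficacy of the initial and maintenance regimens, and the pooled effect answers that. A reader might infer that the maintenance objective goes unanswered. The documents do not support that: the mismatch is with the wording of Hypothesis 2, not with Aim 1.

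2. Additivity is a visible modelling choice. Section 10.2 conjectures that weekly stimulation has a somewhat smaller effect than daily stimulation, which implies that it works in its own right. If that effect is the same after sham as after active treatment, pooling is correct and more precise. Exact halving needs the extreme case of no weekly effect after sham.

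3. AA-AS is itself ambiguous. If weekly tACS works alone, AA beats AS with nothing prolonged, and AA-AS has about 85% power to show it. It is therefore tempting, but wrong, to let AA-AS alone license a claim of prolonged benefit. Only the difference between AA-AS and SA-SS separates the two.

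4. The plan calls the estimate a direct treatment effect in period 2 and nowhere says it will be reported as prolongation. It describes the maintenance paradigm as exploratory. It also promises goodness-of-fit checks, plots and modified versions of the main analyses. These soften the gap, but none names the contrasts needed.

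The joint primary F-test keeps about 83% power under pure prolongation (d = 1.46, ρ = 0.90), but it does not isolate Hypothesis 2.

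**Conclusion.** The concern holds in a limited form. Every model listed in section 10.2 forces AA-AS to equal SA-SS, so no specified estimate isolates the prolongation in Hypothesis 2. Under pure prolongation the pooled estimate is exactly half the AA-AS difference with equal sequences, whatever the correlation, and the week-1 estimate falls as well. The power figures are less secure: they rest on d = 1.46 from 15 pilot participants, a conjectured 0.90 correlation carried over to t1-t9, and equal variances. The lower value of 0.56 is a confidence limit for the t0-t1 correlation and serves only as a range. The pooled estimate and the joint test remain legitimate. This is a worthwhile, cheap improvement rather than a defect that invalidates the primary analysis.

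**What to change.** In section 10.2, Aim 1:

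- Keep the joint primary F-test and the pooled period-2 estimate. Label the latter as the average effect of weekly tACS regardless of week-1 treatment.
- Add one prespecified {t1, t9} model with sequence-specific means at t9. Report with 95% CIs: AA-AS (the estimate addressing Hypothesis 2), SA-SS, and (AA-AS)-(SA-SS).
- State that AA-AS shows whether maintenance gives a better week-8 outcome after an active course, and that only the difference separates prolongation from a stand-alone effect of weekly tACS. State also that the difference is imprecise (SE about 0.65) and is for estimation, not gatekeeping.

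The cost is SAP wording and one extra fit of data already collected. The AA-AS interval is about 40% wider than the pooled one (SE 0.46 versus 0.32).

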### 10.2 STATISTICAL ANALYSIS PLANS

The following statistical considerations and aim-specific analysis plans will be reviewed and updated prior to any data collection. To help ensure reproducibility and objectivity of the results, these *a priori* plans specify details for the main analyses for each specific aim; e.g., details of fitted models and decisions regarding the units and scales of the measurements of interest. The plans include 1) sensitivity analyses performed to assess the robustness of the major results to reasonable perturbations of the assumptions and methods used; 2) exploratory analyses for hypothesis generation; 3) necessary descriptive graphical and tabular methods used to visualize the data, and 4) exploration of relationships among the variables of interest. Following best practices (e.g., [www.CONSORT-statement.org](http://www.CONSORT-statement.org)), all statistical estimates (e.g., variances, means, differences) will be reported along with their 95% confidence intervals (C.I.s). Hypothesis tests that are observed to be not statistically significant will be reported as being inconclusive. (Hypothesis tests that are not statistically significant are entirely inconclusive and no conclusions can be drawn from those tests. Statistical test procedures are incapable of establishing that the null hypothesis is true.) The word “inconclusive” will be used when reporting a test that was not statistically significant. To avoid over-reliance on p-values, the focus of the analyses will be on the point-estimates and interval-estimates of the magnitudes of the population parameters of interest (e.g. treatment effects).

**Plans for Aim 1:** *Evaluate the relative efficacy of the tACS treatment regimen and subsequent maintenance regimen in terms of changes in the mean level of the AHRS score.*

Clinical scores (AHRS, PANS, BACS) will be recorded on nine occasions (t): at baseline immediately before the first stimulation session on day 1 (t0), after the stimulation session ending day 5 (t1), and after each weekly maintenance session (t2, t3, t4, t5, t6, t7, t8, t9). The experimental design is best viewed as a 2-treatment, 4-sequence (SS, SA, AS, AA), 2-period randomized crossover with longitudinally repeated measures during the second period. Equivalently, it can also be viewed as a 2-treatment, 4-sequence, 9-period crossover.

For AHRS,  $Y_{ij}(t_0)$  is the baseline score from the  $i$ -th participant in the  $j$ -th treatment sequence ( $j = SS, SA, AS, AA$ ). The primary analyses will focus a linear mixed-effects model for the change from baseline on occasion  $t$ ,  $\Delta Y_{ij}(t) = Y_{ij}(t) - Y_{ij}(t_0)$ , conditional on the following explanatory variables: assigned treatment regimen, treatment stage (initial daily stimulation vs maintenance weekly stimulation), and baseline score  $Y_{ij}(t_0)$  as a covariate.

$$[\Delta Y_{ij}(t) | \mathbf{X}, Y_{ij}(t_0)] = \mu_S X_1 + \mu_A X_2 + \tau_S X_3 + \tau_A X_4 + \lambda X_5 + \beta (Y_{ij}(t_0) - \bar{Y}(t_0)) + \varepsilon_i + \varepsilon_{ij}(t)$$

Here,  $\bar{Y}(t_0)$  is the average of all baseline values. The expected value is shown in **Table 1** below. The fitted model will be used to tabulate statistical estimates (all with 95% confidence intervals) of the population parameters of interest: variance components, intra-class correlation, the direct effect of treatment ( $\mu_S - \mu_A$ ) in period 1, treatment-specific period effects ( $\tau_A, \tau_S$ ), and a longer-term treatment effect ( $\lambda$ ) that carries over from period 1 into period 2. Parameters  $\tau_A$  and  $\tau_S$  represent both the period-by-treatment interaction and also the 'period effect' ( $\tau_A + \tau_S$ ). In a 2-sequence crossover design, parameters  $\tau_A, \tau_S$  and  $\lambda$  would be aliased together; whereas, in the 4-sequence design they are not aliased. For the main analysis we assume carryover effect  $\lambda$  vanishes in the later weeks of the maintenance regimen in period 2; that is, effects of any treatments in period 1 have washed out by the end of the maintenance regimen. (That would not be the case if treatment A in period 1 cured the patient.) The sensitivity of the main results to this assumption will be investigated in auxiliary sensitivity analyses. In this model, the direct treatment effect in period 1 is  $(\mu_S - \mu_A)$  while the direct treatment effect in period 2 is  $((\mu_S + \tau_S) - (\mu_A + \tau_A))$ . We conjecture that  $\tau_S \approx 0$  and that  $\tau_A$  has a small negative value owing to weekly stimulation having a somewhat smaller effect than daily stimulation. The magnitude of  $\tau_S$  is of interest because it represents the efficacy of montly stimulation relative to daily stimulation. The magnitude of  $\lambda$  is of interest because it represents impact of treatment that endures into (at least) the beginning of the maintenance regimen.

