### **4 STUDY DESIGN AND OUTCOME MEASURES**

#### **4.1 STUDY OUTCOME MEASURES**

##### **4.1.1 PRIMARY OUTCOME MEASURES**

The Auditory Hallucination Rating Scale (AHRS) will be the primary outcome measure for this study. This survey instrument will be administered at the first recruitment visit, two weeks later at the screening visit, at baseline ( $t_0$ ) on the first day of stimulation, after stimulation on the fifth day of stimulation ( $t_1$ ), and at each of the 8 weekly maintenance sessions ( $t_2, t_3, t_4, t_5, t_6, t_7, t_8, t_9$ ). The primary analyses will focus on longitudinal changes from baseline in the AHRS scores at  $t_1$  and  $t_9$  accounting for the following explanatory variables: treatment regimen, treatment stage (initial daily stimulation vs maintenance weekly stimulation), and the baseline AHRS score as a covariate.

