### 10.3 SAMPLE SIZE CONSIDERATIONS

It is difficult to recruit a large number of patients diagnosed with schizophrenia with persistent auditory hallucinations to participate in a single site extensive study. However, based on our recent experience recruiting for patients with these symptoms, we expect that we can successfully recruit 40 subjects from this population.

We evaluated the performance characteristics of the study design and analysis strategy under the assumption that only 40 subjects will be available. To do this we used information from a previous randomized study conducted in this lab (IRB 14-3285). That study obtained baseline AHRS scores ( $Y_0$ ) and post-treatment AHRS scores ( $Y_1$ ) from participants sampled from our target population using the same methods and inclusion/exclusion criteria.

**Table 2** lists information obtained: 7 patients received sham treatment (**S**), 8 received 10Hz tACS treatment (**A**).

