## 10.4 RANDOMIZATION AND BLINDING

### 10.4.1 ENROLLMENT/ RANDOMIZATION/ MASKING PROCEDURES

Participants will be randomized into one of four treatment-sequence groups. The randomization assignment will occur prior to beginning the initial 5 days of stimulation, once the participant has passed the screening sessions. The randomization will be as follows: tACS and tACS, tACS and sham, sham and sham, sham and tACS. This is a double blind study, so neither the participant nor the researcher will know which treatment treatment-sequence group the participant has been assigned to.

A [name] Lab member ([name]) will randomize 40 codes which will be used by the study coordinator and research assistants. These codes will be randomized prior to recruitment of any participants. These codes are directly linked to which treatment regimens the participants receive (sham (S) or 10Hz tACS (A)).

The codes will be randomized using a randomization function available in MATLAB software. A condition will be included so that the same condition will not be assigned to adjacent participants 3 times in a row. The participant randomization will also be stratified on sex, in that separate randomization schedules will be created for each sex. A total of 40 codes will be randomized for each sex because it is possible that there will be, for example, 35 men and only 5 women.

[name] will have no other responsibility in the study other than providing these randomized codes. The master list containing the condition and the codes will be kept solely by [name].

[name] will provide the study coordinators an Excel document with the blinded randomized codes. This document will remain on the secure lab drive. The study coordinator will enter the participant's study ID next to their randomization code on the first day of stimulation.

(The CONSORT Statement notes that "Allocation concealment is a technique used to prevent selection bias by concealing the allocation sequence from those assigning participants to intervention groups, until the moment of assignment." Randomization without allocation concealment is not reliable randomization.)

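### Randomisation is stratified by sex, but the Aim 1 model and the Aim 2 and 3 analyses that reuse it leave sex out; a minor mismatch that one pre-specified term would remove

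*Combined protocol and SAP*

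**What the plan says.** The Schematic of Study Design states: "The randomization will be stratified by sex". Section 10.4.1 explains how: "The participant randomization will also be stratified on sex, in that separate randomization schedules will be created for each sex". Forty codes are prepared for each sex because "it is possible that there will be, for example, 35 men and only 5 women". The target is 40 participants, with "10 participants per sequence".

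The analysis sections do not carry this through. Section 4.1.1 lists the explanatory variables as "treatment regimen, treatment stage (initial daily stimulation vs maintenance weekly stimulation), and the baseline AHRS score as a covariate", and Section 10.2 conditions the mixed model on "assigned treatment regimen, treatment stage (initial daily stimulation vs maintenance weekly stimulation), and baseline score". The equations in Sections 10.2 and 10.3 (general, primary, carryover and power models) contain indicators for regimen, stage and, where included, carryover, plus centred baseline AHRS. None contains sex. Section 4.1.2 gives a similar covariate list for the secondary outcomes, and Section 10.2 expects the Aim 1 approach to serve Aims 2 and 3. On sensitivity analyses, Section 10.2 says only that the set "will include modified versions of the main analyses", without naming sex.

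**The concern.** A stratified design is normally analysed with the stratification factor in the model. If sex predicts change in AHRS and the lists balance it across sequences, a model without sex leaves that variance in the between-subject error. Standard errors are then somewhat too large. If the lists do not balance sex, the unadjusted estimate moves with whatever imbalance occurs. Imbalance is possible: Section 10.4.1 gives no block size, only part of each 40-code list will be used, one sex may be rare, and only completers are analysed.

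There is also a question of pre-specification. Section 10.2 sets out to fix the details of the fitted models in advance. If sex is first added once results are visible, that becomes a post hoc choice.

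**Working it through.** **Inputs from Section 10.3.** N = 40; inter-subject variance 4.98 (95% limits 2.66 and 12.35); intra-subject variance 0.55 (0.30 and 1.37); alpha 0.025 for the separate test of the first-week contrast μS − μA; true difference 1.18 AHRS points; stated power 90%, interval 50% to 99%.

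**Assumptions, because the documents give no figure.** 30% women; a sex difference δ of 0 to 3 AHRS points in change from baseline, the same at t1 and t9.

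**Step 1: reproduce the stated power.** With 10 per sequence, first-week and maintenance assignments are orthogonal. Generalised least squares on t1 and t9 then gives

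Var(μS − μA) = (4/N) × s² × (1 − r²), where s² = inter + intra and r = inter/s².

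s² = 4.98 + 0.55 = 5.53; r = 4.98/5.53 = 0.9005; variance = 0.1 × 5.53 × (1 − 0.9005²) = 0.1045; SE = 0.3233.

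Non-centrality = 1.18²/0.1045 = 13.32, and F(1, 36) at 0.025 gives power 90.0%. The variance limits give 49.6% and 99.4%. The plan's figures are reproduced by a model without sex.

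**Step 2: leave out a balanced sex effect.** Omission adds 0.3 × 0.7 × δ² = 0.21δ² to the inter-subject variance.

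| δ | Inter-subject variance | SE without sex | Ratio to 0.3233 | Power at 1.18 without sex |
|---|---|---|---|---|
| 0 | 4.98 | 0.3233 | 1.000 | 90.0% |
| 1 | 5.19 | 0.3236 | 1.001 | 89.9% |
| 2 | 5.82 | 0.3244 | 1.003 | 89.8% |
| 3 | 6.87 | 0.3255 | 1.007 | 89.5% |

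With sex in the model (one degree of freedom fewer, F(1, 35)) power is 89.9% throughout. The largest loss is 0.4 points. The cost of adjusting when δ = 0 is 0.1 point.

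The effect is small because the first-week estimate weights the data roughly as t1 − r × t9. A stable between-subject difference mostly cancels when r is 0.90.

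**Step 3: take the sex variance from within 4.98 instead.** If sex explains 0% to 30% of the inter-subject variance, adding it gives power of 89.9% to 90.5% with sex balanced, or with 5 women split 2/1/1/1. With sex heavily confounded with the first-week regimen (2, 2, 8 and 8 women per sequence) power is 89.3% to 89.7%.

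**Step 4: type I error of the joint F-test at 0.05.** In simulations (8,000 runs per setting; 20/20 or 35/5 split by sex; sex explaining 0%, 10% or 30%) the test rejected in 3.9% to 4.8% of null trials without sex and 3.9% to 4.7% with it. These runs omitted the baseline covariate and treated the variance ratio as known.

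**Step 5: a lower residual correlation.** Section 10.3 conjectures 0.90 for the correlation between t0 and t1. If t0, t1 and t9 are all equally correlated at 0.90, the t1–t9 correlation after adjusting for baseline is ρ/(1 + ρ) = 0.90/1.90 = 0.47. Keeping s² = 5.53, the components become 2.62 and 2.91, and SE = √[0.1 × 5.53 × (1 − 0.4737²)] = 0.655. Power at an assumed 2-point effect, alpha 0.025:

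| δ | Without sex | With sex | Loss (points) |
|---|---|---|---|
| 1 | 75.4% | 75.9% | 0.5 |
| 2 | 73.8% | 75.9% | 2.0 |
| 3 | 71.9% | 75.9% | 4.0 |

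**Step 6: chance imbalance.** With sex left wholly to chance, the SD of the difference in proportion of women is √(0.3 × 0.7 × 4/40) = 0.145. The estimate shifts with SD 0.145 × (1 − r) × δ: 0.014δ at r = 0.90, and 0.076δ at r = 0.47.

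**The case against.** The strongest reply is that the omission barely matters to the test actually planned, and Steps 2 to 4 bear that out. The documents give no sex effect. A 3-point sex difference is about twice the pilot difference between tACS and sham (3.75 − 2.29 = 1.46). The only sex split they mention is 35/5, which adds 0.125 × 0.875 × δ² = 0.109δ² rather than 0.21δ². The pilot variance was also estimated without sex, so adding sex variance on top of it (Steps 2 and 5) tends to overstate the loss. All of this stands, and it limits the point to a minor one.

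A reader might infer something stronger: that the primary test is seriously conservative. In a stand-alone day-5 comparison of 20 with 20 (SD 2.35, 30% women, nominal 5%), a 3-point sex difference does lower true size to about 2.3% and power at a 2-point effect to about 63%. Those figures apply only to a period-1 analysis. Section 10.3 shows such an analysis for comparison; the primary analysis is the t1/t9 mixed model with a subject effect.

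A reader might also infer bias or inflated type I error. Neither is supported. Under randomisation, chance imbalance in sex is part of the sampling error that the interval already reflects, and no simulation showed inflation.

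The reply does not show that the plan deals with sex. The unspecified modified versions of the main analyses do not name it, and no section justifies leaving it out.

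**Conclusion.** The mismatch between design and analysis is real but minor. At the plan's variance components, leaving sex out costs under 1% in standard error and less than half a percentage point of power at 1.18 points, with no type I inflation. A visible though modest cost, about 0.5 to 4 points of power at a 2-point effect, needs both a residual t1–t9 correlation near 0.47 and a sex difference of 1 to 3 points. Chance imbalance would then shift the estimate with SD of about 0.08 times the sex difference.

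These sizes rest on an assumed 30% women, assumed sex differences that are constant over time, and balanced sex in the power figures. They concern AHRS only; nothing in the documents allows the same calculation for PANSS, BACS or EEG alpha power. The case for change is that the analysis should match the randomisation and that the choice should be fixed in advance. The validity of the primary test is not in doubt on this ground.

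**What to change.** In Section 10.2, add sex as a fixed main effect to the Aim 1 primary model and its sensitivity versions, and state that the Aim 2 and 3 models include it too. Amend the covariate lists in Sections 4.1.1 and 4.1.2 to agree. Do this before unblinding. A sex-by-treatment term is not advised: with a split such as 35/5 it could not be estimated with useful precision.

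If the sponsor prefers the present model, the lesser alternative is one sentence justifying the omission and a named sex-adjusted sensitivity analysis.

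The cost is one model term and one degree of freedom, about 0.1 percentage point of power if sex has no effect. No change to data collection, sample size or randomisation is needed.
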